A smartphone otoscope (CellScope-Oto) is a pocket-size attachment that employs the technology and light source of a smartphone to capture reproducible images of the ear canal and tympanic membrane. Previous studies with this device demonstrated that images taken with both the smartphone otoscope and a camera-fitted conventional analogue otoscope were equivalent with respect to image quality (IRB00057321)² and that the smartphone otoscope was acceptable as an educational and diagnostic tool to health professional students (IRB00066495). A pilot study with a similar design to this study conducted in two offices of an ambulatory pediatric clinic demonstrated a trend toward decreased antimicrobial prescription filling among families whose children were examined with the smartphone otoscope (IRB00074526) compared to those who were examined with a conventional otoscope. To further assess this trend, we propose an evaluation of the impact of device use on antimicrobial prescribing for children with an otic complaint in a pediatric emergency department (PED) setting.

We hypothesize that use of a smartphone otoscope with the capability to capture still images and video will reduce the rate of antimicrobial prescribing by emergency department clinicians for otic complaints in children presenting for care in pediatric emergency department settings.

The Pediatric Emergency Department Oto Study (PED-Oto) will be conducted as a

randomized control study in two affiliated children's hospital emergency departments. Twenty volunteer clinicians will be randomly assigned to use either a smartphone otoscope or a conventional otoscope for all otic examinations for a 6-month period. Study outcomes will include:

- 1) rates of antimicrobial prescribing by the clinicians randomly assigned to use a smartphone otoscope compared to the rates of antimicrobial prescribing by the clinicians using a conventional otoscope.
- 2) rates of otitis media or otitis externa diagnoses by the clinicians randomly assigned to use a smartphone otoscope compared to the rates of otitis media or otitis externa diagnoses by the clinicians using a conventional otoscope.
- 3) clinician acceptability of the assigned otoscopic device.

Data will be abstracted via retrospective review of the electronic medical record of encounters in which an otoscopic exam was performed as part of the diagnostic evaluation. We plan to enroll 20 clinicians for the 6-month study period; 10 who will be randomly assigned to use a smartphone otoscope for the 6-month study period and 10 who will be assigned to use a conventional otoscope for all otoscopic exams. Use of a smartphone otoscope has the potential to optimize clinician ability to manage otic complaints, visualize the tympanic membrane, and support antimicrobial stewardship.

3. Introduction and Background:

Acute otitis media (AOM), defined as acute inflammation in the middle ear, is a leading cause of health encounters and antimicrobial prescriptions in children worldwide. In the first three years of life, 80% of children will have one or more episodes of AOM incurring burden to both the individual and the healthcare system. The diagnosis of AOM is often dependent on a brief glance into an uncooperative child's ear canal and incomplete visualization of a tympanic membrane that may be suboptimal for diagnosis. Improved methods of visualizing the tympanic membrane including the capability of capturing still images and video otoscopy (ear exam) have demonstrated an impact on the management of children with otic complaints.

In February of 2013, The American Academy of Pediatrics (AAP) and American Academy of Family Physicians (AAFP) released revised clinical practice guidelines for the diagnosis and management of uncomplicated AOM in children that emphasize visualization of the tympanic membrane in making a clinical diagnosis of AOM. The guidelines further recommended judicious use of antimicrobials and advocates for active and ongoing involvement by both clinician and parent¹.

A pocket-size smartphone attachment that employs the technology and light source of a smartphone to capture reproducible images of the external ear canal and tympanic membrane was developed. Images and video capture of multiple images improves diagnostic capability facilitating a more complete view of the tympanic membrane and optimizing three-dimensional image capture. Digital images captured with the device may be incorporated into electronic medical records, facilitating documentation and review over time, an important aspect in the management of pediatric otic conditions.

The smartphone otoscope device has been evaluated in several settings to assess

function and application. A single-center prospective study published in 2015 (IRB00057321)² found that images from the smartphone otoscope device were of comparable quality to those obtained from a camera-fitted device when subsequently reviewed by blinded pediatricians, emergency medicine pediatricians, and an otolaryngologist. The majority felt photographic documentation for diagnosing acute otitis media would reinforce their decision to defer antibiotic administration. A second study assessing acceptability of a smartphone otoscope compared to a conventional wall-mounted otoscope among medical students, nurse practitioner students, and physician-assistant students noted support for the smartphone device for both learning how to conduct the otic exam and for future patient care (IRB00066495). The students concurred that the smartphone otoscope enhanced tympanic membrane view and diagnostic precision, was easy to use, and preferred it over a traditional otoscope when using the devices to examine each other in an educational setting. A study among resident and attending physicians found good correlation between otitis media diagnoses when resident and attending physicians used conventional and smartphone otoscopes in an emergency department setting³. The physicians also agreed that the smartphone otoscope enhanced tympanic membrane view and diagnostic precision, was easy to use, and preferred it over a traditional otoscope. A study conducted in a neurotrauma clinic found a preference for a smartphone otoscope for use in medical education and diagnostic capabilities⁴.

This study has two proposed hypotheses and subsequent aims:

Hypothesis 1: Use of a smartphone otoscope by pediatric clinicians in a pediatric emergency department setting for otic examinations will result in decreased rates of antimicrobial prescribing for presumptive otic infections, compared to rates of providers using a conventional otoscope.

Specific Aim 1: To compare antimicrobial prescribing practices for otitis media among pediatric emergency care clinicians, we will perform a randomized control trial study in which pediatric clinicians will be randomly assigned to use either a smartphone otoscope or a conventional otoscope for 6 months when an otic examination is performed.

Hypothesis 2: Pediatric emergency care clinicians will express a greater acceptability for use of a smartphone otoscope for the examination of children than use of a conventional otoscope.

Specific Aim 2: To compare pediatric emergency department clinician acceptability of use of a smartphone otoscope with that of a conventional otoscope, we will assess clinician satisfaction and challenges experienced with each device during the study period with a written questionnaire.

4. Objectives:

To address the specific aims stated above, we will utilize a **randomized control study design** to compare antimicrobial prescribing practices of pediatric emergency department clinicians for encounters in which an otic examination is performed while using the smartphone otoscope to those clinicians using a conventional otoscope. (*Specific Aim 1*). Pediatric emergency care clinicians will be surveyed to assess acceptability of smartphone otoscope use compared to conventional otoscope use during the 6-month study period (*Specific Aim 2*).

5. Study Design and Methods:

We propose a randomized, controlled study. The smartphone otoscope will be used in clinical care in the same manner as a conventional otoscope. Twenty volunteer Pediatric Emergency Department clinicians will be randomized to use either the smartphone otoscope or a conventional otoscope for 6 months for all non-traumatic patient otoscopy (ear examinations). In the event that a clinician assigned to use the smartphone otoscope device is unable to use the assigned smartphone otoscope device, s/he will be able to use a conventional otoscope for the examination that cannot be completed with the smartphone otoscope, with documentation to the study team of the reason that the smartphone otoscope could not be used on a study log. The study log, stored in a locked file cabinet, will be reviewed by a member of the study staff in real time to troubleshoot equipment challenges and to monitor study progression. The option to use a conventional otoscope device by clinicians assigned to use of the smartphone device will ensure that clinical care is not adversely impacted in the event of smartphone device malfunction or another situation that makes smartphone otoscope device not feasible.

All encounters in which an otic examination is performed for a non-traumatic chief complaint will be considered to be eligible to be included in the study. Eligible encounters will be tracked by having the clinician place a patient identification sticker on a log sheet. The log sheet will contain the physician study ID number, date and times of shift, patient sticker and a notation if a clinician substituted a conventional otoscope for the smartphone otoscope device. The study log sheet will be stored in a locked file cabinet, accessible only to study staff. The electronic medical record will be retrospectively accessed, based on the medical record number listed on the study log sheet to collect study-relevant information (**PED-Oto EMR Abstraction Form**) including age of patient, history of otitis diagnoses, past antimicrobial prescription use, antimicrobial prescribed, duration of antimicrobial prescribed, and instructions given specifying the conditions under which to initiate an antimicrobial, if given. Personal identifiers will be maintained only as necessary to link the encounter to the medical record for extraction of study-related information. All information will be recorded in a password protected electronic database. Paper copies of the study log will be stored in a locked file cabinet. Access to both electronic and paper copies of study information will only be granted to study staff.

Information collected as part of the PED-Oto study:

1. Line listing of patients seen per shift by participating study clinicians and record

of device substitution, **PED-Oto Device Use**.

2. Electronic record medical record review of encounters in which an otoscope device was used as reported by study-participant clinicians. Encounters related to ear trauma will be excluded. The **PED-Oto EMR Abstraction Form** will be completed retrospectively by a member of the study staff.
3. At the conclusion of the 6 month study period, the 10 pediatric emergency department clinicians randomly assigned to use the smartphone otoscope device will complete a written questionnaire to assess their comfort level, ease of use, and preference for or against the otoscope device. This assessment will be known as the **PED-Oto Clinician Assessment**.

6. Participant selection:

The subjects in this study will be 20 randomly selected pediatric emergency care clinicians who perform care at one or both locations (Egleston or Hughes Spalding) of a tertiary care pediatric hospital system. Subjects will agree to random assignment to either a smartphone otoscope device or a conventional otoscope device for the 6-month study period. Informed consent will be obtained from each participating clinician prior to the initiation of the study by a member of the study staff. Study participants will be asked to: 1) compile a list of patient encounters that included an otoscopic examination for a non-traumatic indication for each shift worked during the study period, 2) document and report episodes of care in which the assigned otoscopic device could not be used on a study-eligible otoscopic examination, 3) the 10 clinicians assigned to use the smartphone otoscope will be asked to complete an end of study assessment, the **PED-Oto Clinician Assessment**.

This study presents no more than minimal risk to the subjects. The greatest risk is the loss of privacy by the participating clinicians. There is likely no direct benefit from participation in the study for the individual clinicians. Clinicians assigned to the smartphone otoscope arm will be permitted to keep the clip-on otoscopic device, without the loaned iPhone, as compensation (approximate retail value \$79) for the time and effort related to instruction of device use and completion of study-related documentation. Clinicians assigned to use a conventional otoscope will be given a \$50 gift card at the completion of the study period. Completion of the 6-month study period will be required for compensation.

7. Statistical analysis:

Statistical analyses will predominantly be descriptive with assessments of means, medians, standard deviations, and statistical tests to correlate device and rates of antimicrobial prescribing practices within and among clinicians. Twenty clinicians (10 assigned to the smartphone otoscope intervention and 10 to conventional otoscopy) will participate in the six month study, with a combined 1000 encounters over the 6-month study period. Allowing for drop out, incomplete data collection and other study related issues, we anticipate that we will have usable assessments from 800 encounters.

8. Adverse event reporting:

As this study does not pose more than a minimal risk to subjects, it is unlikely that there

will be a need to discontinue the study due to adverse effects. Rates of completed clinician assessments as well as reports of study related issues will be reported in real time to study staff. Adverse events will be recorded and reported using standard IRB documentation. Progress reports for each 6-month study period will be presented as requested from the funding source.

9. Data and safety monitoring plan (DSMP):

The data safety and monitoring plan will consist of periodic review of the clinician assessments by study staff during which research and study issues will be reviewed. Due to the minimal risk nature of the study, an independent data and safety monitoring committee will not be convened. Standards for stopping procedures will be observed in the case of an adverse event. Study staff will immediately be convened and the issues will be addressed on an urgent basis.

10. Device information:

The device is manufactured by CellScope, Inc. The device is not FDA approved for the indication and there is no IDE. The trade name is the CellScope-Oto and it is considered to be a non-significant risk device. This device is class 1, 510(k) exempt. 21 CFR Part 874 (ear, nose, and throat devices) includes Regulation Number 874.4770 (Otoscope), a Class I, 510(k) exempt device only when used in the external ear canal. When used in the external ear canal, a premarket notification application and FDA clearance is not required before marketing an otoscope in the U.S. This is a reusable device that is used with a single use disposable ear tip that is placed in the external ear canal. The research team is responsible for device maintenance. Any parts of the device having contact with human subjects will be topically disinfected between subject use or discarded after single use. The study team or clinician will keep the device on the person or locked in a research team office. The study team is responsible for tracking use of the device and dispensing the device.

References:

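### Prescribing and diagnosis rates are taken over encounters in which the clinician chose, after randomisation, to examine the ear; the plan needs a check on examination frequency and a comparison on a denominator fixed before the examination

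*Combined protocol and SAP*

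**What the plan says.** Clinicians are randomised, and each knows which otoscope he or she has been given. Section 5 (Study Design and Methods) then states which encounters count: "All encounters in which an otic examination is performed for a non-traumatic chief complaint will be considered to be eligible". The summary describes the data source in the same terms, as a "retrospective review of the electronic medical record of encounters in which an otoscopic exam was performed as part of the diagnostic evaluation". Section 4 (Objectives) compares prescribing "for encounters in which an otic examination is performed while using the smartphone otoscope to those clinicians using a conventional otoscope".

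The outcomes are listed in the summary as "rates of antimicrobial prescribing by the clinicians randomly assigned to use a smartphone otoscope" and "rates of otitis media or otitis externa diagnoses by the clinicians randomly assigned to use a smartphone otoscope", each against the conventional arm. Neither has a written denominator.

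Clinicians identify eligible encounters themselves by placing a patient sticker on a log sheet, and records are abstracted for the logged encounters. Item 1 of the information to be collected (Section 5) is a "Line listing of patients seen per shift by participating study clinicians", with device substitutions. Section 6 (Participant selection), however, asks clinicians to list only encounters that included an otoscopic examination. No analysis uses a count of all patients seen. Nothing in the plan says when an ear should be examined, and no comparison of examination frequency between arms is planned.

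**The concern.** Randomising clinicians makes the arms comparable in the patients who reach them. It does not make them comparable in the subset selected later by a decision that the device itself may influence. A convenient imaging device might prompt more looks at children with little suspicion of ear disease, and those children would enlarge the denominator while adding few or no prescriptions. The smartphone arm would then show a lower rate even if every kind of child, once examined, were managed exactly as in the other arm. That pattern would look like support for Hypothesis 1. A device that discouraged looking would push the rate the other way. The same applies to the diagnosis rate.

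This is separate from logging error. If every examination were logged, and the log were audited against the record, the two denominators could still contain different mixes of children.

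**Working it through.** **The plan's own figures.** Section 7 expects 1000 encounters, of which 800 are usable, from 20 clinicians. 800 = 1000 × (1 − 0.20), so the implied loss is 20%. Per clinician this is 1000/20 = 50 planned and 800/20 = 40 usable encounters. These are expected volumes, not the result of a power calculation. The documents give no base rate, effect size, alpha, intracluster correlation (ICC) or number of patients seen, so every rate below is an assumption.

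**What the shift does to the rate.** Let p be the per-examination rate in the conventional arm, x the proportional change in examinations in the smartphone arm, and f the prescribing rate in the added (or omitted) children as a fraction of p. Then

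smartphone-arm rate = p(1 + fx)/(1 + x).

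Take p = 20/70 = 28.6%: of 100 relevant children, 70 are examined and 20 prescribed for.

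| Change in examinations (x) | f = 0 (none prescribed) | f = 0.5 (half the base rate) |
|---|---|---|
| +10% | 26.0% (−9%) | 27.3% (−5%) |
| +20% | 23.8% (−17%) | 26.2% (−8%) |
| +30% | 22.0% (−23%) | 25.3% (−12%) |
| −20% | 35.7% (+25%) | 32.1% (+13%) |

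Relative changes are in brackets. At x = +20% there are 84 examinations. With f = 0 the rate is 20/84 = 23.8%. With f = 0.5 it is (20 + 14 × 0.143)/84 = 22/84 = 26.2%. In that second case prescriptions per 100 children go up, from 20 to 22, while the per-examination rate goes down. With f = 1 the rate does not move.

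**The same data on two denominators.** Suppose each arm sees 1000 comparable children and writes 120 prescriptions, with 400 ears examined in the conventional arm and 500 in the smartphone arm. Per examination: 120/400 = 30.0% against 120/500 = 24.0%. Per patient seen: 120/1000 = 12.0% in both arms.

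**Chance of a false reduction.** Section 7 names no test, so a two-sided 5% t-test on clinician rates is assumed, with 10 clinicians per arm, 40 encounters each and beta-binomial counts (40,000 simulated trials). The chance of a significant fall should be about 2.5%.

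| Scenario | ICC 0.10 | ICC 0.05 | ICC 0.01 |
|---|---|---|---|
| +20% examinations, f = 0 | about 10% | 13% | 23% |
| +20% examinations, f = 0.5 | 5% | 6% | 9% |
| +10% examinations, f = 0.5 | 4% | 4% | 5% |

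**Precision of a per-patient rate.** With n = 40 and p = 28.6%, (1 − p)/p = 2.5. The relative variance of one clinician's per-examination rate is 2.5(1 + 39·ICC)/40. For prescriptions per patient seen, with Poisson examination counts, it is 1/(np) + 2.5·ICC = 0.0875 + 2.5·ICC. At ICC 0.10 these are 0.306 and 0.338 (+10%); at ICC 0.01 they are 0.087 and 0.113 (about +30%). If clinicians also vary in examinations per patient seen with an assumed coefficient of variation of 30%, 0.09(1 + 2.5·ICC) is added. The relative variance then rises by about 47%, 70% and 136% at ICC 0.10, 0.05 and 0.01.

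**The case against.** The strongest reply is that no passage shows the device altering how often ears are examined. Section 3 reports that earlier users found it easy to use and preferred it, which concerns liking rather than frequency, and Section 5 says it is to be used in the same manner as a conventional otoscope. This stands: the mechanism is plausible, not shown, and its direction is unknown.

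Second, the larger figures need every added child to go untreated. This also stands. At half the base rate the distortion is halved, and the false-positive chances come much closer to nominal.

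Third, Section 5 lets a smartphone clinician switch to a conventional otoscope when the device cannot be used, and the log records the substitution. A difficult device therefore need not remove the encounter from the denominator, so a loss of examinations in that arm is the less likely route. The provision does not reach the decision whether to examine at all, so it gives no protection against extra examinations.

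Fourth, the denominator is inferred. That is true, but the eligibility rule, the objective and the abstraction source agree, and the planned data collection supports no other.

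A reader might go further and conclude that prescriptions per patient seen should replace the per-examination rate as the main outcome, at little cost in precision and with the line listing supplying the count. The documents do not support this. Aim 1 concerns care when an otic examination is performed, the variance calculation shows a material loss of precision with 10 clinicians per arm, and Section 6 suggests that the listing holds only examined patients.

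**Conclusion.** The point holds in a limited form. The plan, followed as written, compares rates in a set selected after randomisation by clinicians who know their device, and it contains nothing that would reveal whether the device changed that selection. If it did, the per-examination rates could move without any change in how a given child is managed. Under the assumed 28.6% base rate and 20% more examinations, the apparent fall is between about 8% and 17% relative, depending on whether the added children are prescribed at half the base rate or not at all. If the device leaves the decision to examine unchanged, or if added children are prescribed at the base rate, this bias is absent.

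It should not be read as showing that the comparison is biased, or that a positive result would be an artefact. Nor does it make the per-examination rate the wrong quantity to report. What is missing is a cheap safeguard that lets the two explanations be told apart.

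**What to change.** In Sections 5 and 7, keep the per-examination prescribing and diagnosis rates, write out their denominators, and add:

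1. Ear examinations per 100 non-trauma patients seen, by assigned arm.
2. A prespecified clinician-level comparison by assigned arm of otic antimicrobial prescriptions and of otitis media or externa diagnoses, on a denominator fixed before the examination. This can be all non-trauma patients seen, or those with a prespecified presenting complaint such as an ear complaint. The narrower set is closer to the otic-complaint population described in the summary.
3. An interpretation rule: a difference per examination that is not matched in comparison 2 will not be read as reduced prescribing.

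Take the denominator, prescriptions and diagnoses for comparison 2 from the emergency department record, for every shift worked. Identify shifts from rosters rather than from the log: a shift with no logged examination may be absent from the log, and such absences depend on the same decision to examine. State also whether the line listing covers all patients seen or only those examined.

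The cost is one additional record query, linked to shift rosters, and some wording. Comparison 2 will be less precise than the per-examination rate, because clinicians vary in how many of their patients need an ear examination; it should be reported with a confidence interval and read with that in mind.

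### Patient age, otitis history and past antimicrobial use are abstracted for each logged encounter, but Section 7 gives them no role and specifies no adjustment

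*Combined protocol and SAP*

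**What the plan says.** Section 5 (Study Design and Methods) has clinicians log each non-traumatic encounter that includes an ear examination. Staff then open the medical record "based on the medical record number listed on the study log sheet to collect study-relevant information". Among the items abstracted are "age of patient, history of otitis diagnoses, past antimicrobial prescription use".

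The first study outcome in the opening summary is "rates of antimicrobial prescribing by the clinicians randomly assigned to use a smartphone otoscope compared to the rates of antimicrobial prescribing" in the conventional arm. Section 7 (Statistical analysis) says that the analysis will be mainly descriptive, with "statistical tests to correlate device and rates of antimicrobial prescribing practices within and among clinicians". It names no covariate, regression model, stratification or adjusted estimate. No other section gives a use for the three variables.

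Section 7 gives the allocation as "Twenty clinicians (10 assigned to the smartphone otoscope intervention and 10 to conventional otoscopy") and the size as 20 clinicians "with a combined 1000 encounters over the 6-month study period", of which "we anticipate that we will have usable assessments from 800 encounters". Under Section 6 the clinicians "perform care at one or both locations (Egleston or Hughes Spalding"), and no stratification of the randomisation by site is described.

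**The concern.** Children reach a clinician through site and shift, so case mix is balanced only by randomising 20 clinicians. Age, otitis history and past antimicrobial use plausibly predict whether an antimicrobial is prescribed. If they do, a difference in case mix between two groups of 10 clinicians moves the observed prescribing difference for reasons unrelated to the otoscope, and it adds to the variation between clinicians.

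Adjusting for patient-level values fixed before the encounter removes that part of the variation at almost no cost in clinician-level degrees of freedom. If the plan stays silent, the decision to adjust, and the choice of covariates, can be made after the results of an open-label study are known.

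**Working it through.** **The plan's own figures.** There is no power calculation to reproduce, because no alpha, effect size, control rate or ICC is stated. The counts are consistent: 1 − 800/1000 = 20% loss, 1000/20 = 50 planned and 800/20 = 40 usable encounters per clinician, or 400 per arm if equal.

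**Inputs.** From Section 7: 10 clinicians per arm and 40 usable encounters each (taken as equal). Assumed, because the documents give no values: a binary covariate present in 40% of encounters, covariate ICC within clinician of 0 to 0.05, and a 15 to 25 point difference in prescribing between children with and without it.

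**Step 1: chance imbalance.** SD of the between-arm gap in the covariate = sqrt(0.40 × 0.60 × [ICC + (1 − ICC)/40]) × sqrt(2/10).

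| Covariate ICC | Calculation | SD of gap | Chance of a gap over 10 points |
|---|---|---|---|
| 0 | sqrt(0.24 × 0.02500) × 0.447 | 3.5 points | 0.4% |
| 0.02 | sqrt(0.24 × 0.04450) × 0.447 | 4.6 points | not calculated |
| 0.05 | sqrt(0.24 × 0.07375) × 0.447 | 5.9 points | 9% |

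**Step 2: shift in the prescribing difference.** Shift SD = SD of gap × prescribing difference. The low end is 3.5 × 0.15 = 0.5 points and the high end is 5.9 × 0.25 = 1.5 points.

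**Step 3: wider assumptions.** With prevalence 30% to 50% and a prescribing difference of 10 to 30 points, the 95% range of the shift is ±0.6 to 2.1 points at covariate ICC 0, ±1.1 to 3.6 at 0.05, and ±1.4 to 4.6 at 0.10.

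**Step 4: what adjustment buys.** Simulation of 4,000 trials per setting: 10 against 10 clinicians, 40 encounters each, control rate 30%, covariate prevalence 40%, prescribing difference 25 points, outcome ICC about 0.03, true reduction 10 points. The test is a clinician-level t-test, with or without correction of each clinician's mean by the within-clinician covariate slope.

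| Covariate ICC | SD of estimate, unadjusted to adjusted | Power, unadjusted to adjusted |
|---|---|---|
| 0.01 | 4.6 to 4.5 points | 52% to 54% |
| 0.05 | 4.7 to 4.5 points | 51% to 55% |
| 0.10 (sensitivity) | 4.8 to 4.4 points | 49% to 55% |

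With no true effect, both tests rejected about 5% of the time and the mean estimate was close to zero. The two calculations agree: at covariate ICC 0.05 under no effect the SD fell from 4.88 to 4.65 points, and sqrt(4.88² − 4.65²) = 1.5, the high-end shift from Step 2.

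**The case against.** Several objections carry weight.

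- **Section 7 does not rule adjustment out.** A reader might infer that the plan commits to a raw comparison of rates. It does not say so; the tests are simply unnamed. The supportable statement is that no adjustment is specified.
- **Chance imbalance is not bias.** A reader might infer that the result will be biased. Under randomisation of clinicians, chance imbalance averages out, and a clinician-level analysis already carries it in its standard error. This stands: what is lost is precision, together with a shift in the single realised estimate.
- **The gain is small.** A shift SD of 0.5 to 1.5 points sits beside a standard error of about 4.6 to 4.7 points. The simulated gain uses the top of the assumed 15 to 25 point range, and the 6-point gain needs a covariate ICC above 0.05. This also stands. However, the figures are for one covariate and three are collected.
- **The covariates are loosely defined.** Past antimicrobial use has no look-back window, so its prevalence and predictive strength could differ widely from those assumed. Section 7 itself expects incomplete data.
- **Imbalance may not be due to chance alone.** Clinicians know their device and decide what they log. A reader might infer that adjustment would repair selective logging; three covariates cannot be relied on to do so fully.
- **Clustering matters more.** No clustered method is named. In the same simulation, an encounter-level test that ignored clinicians rejected a true null 19% to 22% of the time. The fix must therefore include clustering, but naming a clustered test would still leave the covariate question open.

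**Conclusion.** The point holds as a modest improvement to the analysis. The plan collects three plausible pre-encounter predictors of prescribing and gives them no role. The cost of leaving them out is a chance shift with an SD of about 0.5 to 1.5 points from one covariate, and about 2 to 4 points of power at covariate ICC 0.01 to 0.05. It is not a validity error, provided that the comparison respects clinician clustering.

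The existence of the gap rests on the text alone. Its size rests wholly on assumed prevalence, ICCs, control rate and predictive strength. In the simulated setting, power is close to 50%, so even a small gain is worth taking when the data are already being abstracted.

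**What to change.** Amend Section 7 to state the following.

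1. **Primary comparison.** Prescribing is compared by assigned arm on the risk-difference scale, so that the adjusted and unadjusted results estimate comparable quantities. Use either a linear mixed model with a clinician random effect and small-sample degrees of freedom, or a two-stage analysis that compares covariate-corrected clinician means (10 + 10 − 2 = 18 degrees of freedom before any clinician-level covariate).
2. **Covariates.** Patient age, history of otitis diagnoses and past antimicrobial use. Each is coded as of before the index encounter, so that the index diagnosis and prescription, which are outcomes, cannot enter as history. Give a look-back window for past antimicrobial use.
3. **Site.** Adjust for encounter site where it is recorded. For clinicians who work at one location only, site acts as a clinician-level covariate; with 20 clinicians, add few others of that kind.
4. **Missing covariates.** State one simple rule in advance, for example a separate category for an undocumented history item.
5. **Reporting.** Give the unadjusted clinician-level risk difference beside the adjusted one, and tabulate the covariates by arm. State that adjustment does not fully correct selective logging.

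The cost is analysis wording plus coding definitions for the abstraction form. No extra clinicians, encounters or categories of data are needed.
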